8.5 Examination of Subgroups

Subgroup analyses will be conducted as stated in the exploratory analysis sections. It should be noted that the study was not designed to detect treatment differences within subgroups. The following subgroups will be assessed and described within the exploratory analysis sections (a minimum of 50 patients will be required for each subgroups).

For the primary objective (the pattern of NOAC usage):

- Sex:
 - Female
 - Male
- Age at the time of the study visit:
 - 75-79 years
 - 80-84 years
 - ≥ 85 years
- Presence of each comorbidities at the time of the study visit (heart failure, coronary artery disease, peripheral vascular disease diabetes, chronic kidney disease, liver disease, cancer):
 - No
 - Yes

For the secondary objectives (Patient's characteristics at the time of the study visit and OAC treatment management):

- Duration since the first NOAC initiation date until the study visit:

Document:	H:\HOR-Europe\2019\2512352 - Study on anticoagulation management - BI\Proyecto\Estadistica\SAP\S		
	AP_REBELD_version1.0_08072020.docx		
Author:	██████████	Version Number:	Version 1.0
		Version Date:	[08072020]

Template No.: RWI_TP_BIOS0013 Revision 1

Reference: RWI_WI_BIOS0015

Effective Date: 15Jun2018

- ≤4 months
- > 4 months

9. OUTPUT PRESENTATIONS

Tables and Figures on page 42 describe the presentations for this study and therefore the format and content of the summary TLFs to be provided by [REDACTED]

10. DISPOSITION AND WITHDRAWALS

All subjects who provide informed consent will be accounted for in this study.

Subject disposition, withdrawals, and protocol violations (as defined in section 6.2), including inclusion and exclusion criteria will be presented for all enrolled patients.

11. DEMOGRAPHIC AND OTHER BASELINE CHARACTERISTICS

Demographic data and other baseline characteristics will be presented for the FAS.

The following demographic and other baseline characteristics, related to secondary outcome, will be collected from medical records or at study visit to describe the patient's characteristics:

Table 3. Patient characteristics at the time of study visit

Variable	Obtained from medical records	Obtained at the study visit
Demographic characteristics: Age, sex, height, weight, BMI, caregiver (Yes/No), place where patient is living (Home alone; At home with	x	x

Document: H:\HOR-Europe\2019\2512352 - Study on anticoagulation management - BI\Proyecto\Estadistica\SAP\SAP_REBELD_version1.0_08072020.docx

Author: [REDACTED] Version Number: Version 1.0
Version Date: [08072020]

Template No.: RWI_TP_BIOS0013 Revision 1

Reference: RWI_WI_BIOS0015

Effective Date: 15Jun2018

Variable	Obtained from medical records	Obtained at the study visit
partner/other family member/a friend; Other's home (e.g family member's); Nursing home)		
Smoking habit (past/current/non-smoker) and alcohol consumption (casual or non-consumer/habitual/abuse/dependence)	x	x
Analytical lab results (from last available blood sample analysis): - Kidney function: serum creatinine (mg/dl), creatinine clearance (Cockcroft-Gault calculation) - Liver function: AST/ALT (UI/L), total bilirubin (mg/dl) - Haemoglobin (g/dl) and platelet levels (x uL)	x	
NVAF: - Diagnosis date (month and year) - Type (persistent, long standing persistent, permanent, paroxysmal) - Modified EHRA scale for AF related symptoms	x	x (mEHRA scale)
Procedures and interventions: - Cardioversion/Ablation (Yes/No) - Coronary interventions (Yes/No): Percutaneous coronary intervention (PCI)/Coronary Artery Bypass Grafting (CABG) - Pacemaker carrier (Yes/No)	x	

Document: H:\HOR-Europe\2019\2512352 - Study on anticoagulation management - BI\Proyecto\Estadistica\SAP\S AP_REBELD_version1.0_08072020.docx

Author: [REDACTED] Version Number: Version 1.0
Version Date: [08072020]

Template No.: RWI_TP_BIOS0013 Revision 1

Reference: RWI_WI_BIOS0015

Effective Date: 15Jun2018

Variable	Obtained from medical records	Obtained at the study visit
Comorbidities and Clinical Risk Factors: - Heart Failure (Yes/No, New York Heart Association (NYHA) classification; Left Ventricular Ejection Fraction, LVEF, %) - Coronary artery disease (Yes/No) - Sleep apnoea-hypopnoea syndrome (SAHS) (Yes/No) - Hypertension (Yes/No) -Hyperlipidemia (Yes/No) - Comorbidity Charlson index (Yes/No; total score): myocardial infarction (already collected for history of thromboembolic events), congestive heart failure (already collected for the NYHA scale scoring), cerebral and peripheral vascular disease, dementia, chronic obstructive pulmonary disease, connective tissue disease, peptic ulcer disease, mild/moderate/severe liver disease, diabetes, diabetes with end-organ damage, hemiplegia, moderate/severe renal disease, any solid tumor, metastatic solid tumor, leukemia, lymphoma AIDs, age (already collected as a demographic characteristic). -History of thromboembolic events (Yes/No, number and date): TIA, ischemic stroke, hemorrhagic stroke, embolism systemic, deep vein thrombosis, pulmonary embolism, stable angina, unstable angina, myocardial infarction with/without ST segment elevation; and bleeding events (Yes/No, number and date): intracranial, digestive, genitourinary, gingival, nasal, pulmonary, articular-muscular, conjunctival.	x	x (NYHA classification, Charlson Index)
CHA2DS2-VASc (total score)		x
HAS-BLED (total score)		x
Clinical Frailty Scale		x
Previous vitamin K antagonist (VKA) treatment (yes/no), type (acenocoumarol or warfarin), start date and treatment duration		
Other concomitant treatments (Total number of current concomitant drugs; Type (Yes/No, number): ARB or ACE inhibitor, Beta-blocker, Calcium channel blockers, Diuretics, Amiodarone, Statin, Proton pump inhibitor, H2-receptor antagonist, Digoxin, NSAIDs, Dronedarone, Other antiarrhythmics, ketoconazole (systemic), cyclosporine, itraconazole	x	

Document: H:\HOR-Europe\2019\2512352 - Study on anticoagulation management - BI\Proyecto\Estadística\SAP\S AP_REBELD_version1.0_08072020.docx

Author: [REDACTED] Version Number: Version 1.0
Version Date: [08072020]

Template No.: RWI_TP_BIOS0013 Revision 1

Reference: RWI_WI_BIOS0015

Effective Date: 15Jun2018

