9.3.3 Covariates

The following covariates, related to the secondary outcome, will be collected from medical records or at the study visit (refer to [section 9.4](#)) to describe the patient's characteristics:

Table 3 Patient characteristics at the time of the study visit

Variable*	Obtained from medical records	Obtained at the study visit
Demographic characteristics: Age, sex, height, weight, BMI, caregiver (Yes/No), place where patient is living (Home alone; At home with partner/other family member/a friend; Other's home (e.g family member's); Nursing home)	x	x
Smoking habit (past/current/non-smoker) and alcohol consumption (casual/habitual/abuse/dependence)	x	x
Analytical lab results (from last available blood sample analysis): - Kidney function: serum creatinine (mg/dl), creatinine clearance (Cockcroft-Gault calculation) - Liver function: AST/ALT, total bilirubin - Hemoglobin and platelet levels	x	
NVAF: - Diagnosis date (month and year) - Type (persistent, long standing persistent, permanent, paroxysmal) - Modified EHRA scale for AF related symptoms (23) (Refer to Annex 3).	x	x (mEHRA scale)
Procedures and interventions: - Cardioversion/Ablation (Yes/No) - Coronary interventions (Yes/No): Percutaneous coronary intervention (PCI)/Coronary Artery Bypass Grafting (CABG) - Pacemaker carrier (Yes/No)	x	
History of thromboembolic events (Yes/No, number): TIA, ischemic stroke, hemorrhagic stroke, embolism systemic, deep vein thrombosis, pulmonary embolism, stable angina, unstable angina, myocardial infarction with/without ST segment elevation; and bleeding events (Yes/No): intracranial, digestive, genitourinary, gingival, nasal, pulmonary, articular-muscular, conjunctival.	x	
Other concomitant treatments (Total number of current concomitant drugs; Type (Yes/No, number): ARB or ACE inhibitor, Beta-blocker, Calcium channel blockers, Diuretics, Amiodarone, Statin, Proton pump inhibitor, H2-	x	

Variable*	Obtained from medical records	Obtained at the study visit
receptor antagonist, , Digoxin, NSAIDs, Verapamil / Dronedaron, Other antiarrhythmics, ketoconazole systemic), ciclosporine, itraconazol)		

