14.6 Exploratory analysis

History and current antiplatelet treatment will be described by current NOAC type.

Treatment received at the time of thromboembolic and bleeding events will be described, including NOAC, VKA and antiplatelet treatments.

Doses of current NOAC treatment received by the patient will be described according to HAS-BLED score (as low, intermediate and high risk).

The percentage of underdosed and overdosed patients for current NOAC treatment will be described.

HAS-BLED total score (as <3 , $3-5$, ≥ 5) will be described according to NOAC and antiplatelet current treatment.

Multivariate logistic regression will be used to evaluate the association between the Clinical Frailty Scale (dependent variable: Frailty patients - CFS scoring >4 vs Non-frailty patients - CFS scoring ≤ 4) and the thromboembolic and the bleeding events (independent variables). To calculate this analysis, only events that have occurred subsequent to the start of anticoagulant therapy (not those prior to the start of VKA / NOACs) will be considered. Other factors will be age, sex, BMI, smoking habit, alcohol consumption, time since NVAf diagnosis, NVAf type, modified EHRA scale, procedures and interventions, comorbidity Charlson index and clinical risk factors. Univariate analysis will be performed. All variables which have a P value of less than 0.1 will be included in the multivariate analysis.

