**Table 13. History of thromboembolic events according to current NOAC type**

		Dabigatran	Rivaroxaban	Apixaban	Edoxaban	Total	Standardized differences (Pradaxa® vs others)
History of thromboembolic events	Valid N No Yes N missing						
Number of total thromboembolic events	Valid N Mean (SD) Median (Q1-Q3) Min-Max N missing						
TIA	Valid N No Yes N missing						
Number of TIA	Valid N Mean (SD) Median (Q1-Q3) Min-Max N missing						
Ischemic stroke	Valid N No Yes N missing						
Number of ischemic strokes	Valid N Mean (SD) Median (Q1-Q3) Min-Max N missing						
Hemorrhagic stroke	Valid N No Yes N missing						

Document: H:\HOR-Europe\2019\2512352 - Study on anticoagulation management - BI\Proyecto\Estadistica\SAP\S AP_REBELD_version1.0_08072020.docx

Author:

Version Number:

Version 1.0

Version Date:

[08072020]

Template No.: RWI_TP_BIOS0013 Revision 1

Reference: RWI_WI_BIOS0015

Effective Date: 15Jun2018

		Dabigatran	Rivaroxaban	Apixaban	Edoxaban	Total	Standardized differences (Pradaxa® vs others)
Number of hemorrhagic strokes	Valid N Mean (SD) Median (Q1-Q3) Min-Max N missing						
Embolism systemic	Valid N No Yes N missing						
Number of embolism systemic	Valid N Mean (SD) Median (Q1-Q3) Min-Max N missing						
Deep vein thrombosis	Valid N No Yes N missing						
Number of deep vein thrombosis	Valid N Mean (SD) Median (Q1-Q3) Min-Max N missing						
Pulmonary embolism	Valid N No Yes N missing						
Number of pulmonary embolisms	Valid N Mean (SD) Median (Q1-Q3) Min-Max N missing						
Stable angina	Valid N No Yes						

Document: H:\HOR-Europe\2019\2512352 - Study on anticoagulation management - BI\Proyecto\Estadistica\SAP\S AP_REBELD_version1.0_08072020.docx

Author: [REDACTED]

Version Number:

Version 1.0

Version Date:

[08072020]

Template No.: RWI_TP_BIOS0013 Revision 1

Reference: RWI_WI_BIOS0015

Effective Date: 15Jun2018

		Dabigatran	Rivaroxaban	Apixaban	Edoxaban	Total	Standardized differences (Pradaxa® vs others)
	N missing						
Number of stable anginas	Valid N Mean (SD) Median (Q1-Q3) Min-Max N missing						
Unstable angina	Valid N No Yes N missing						
Number of unstable anginas	Valid N Mean (SD) Median (Q1-Q3) Min-Max N missing						
Myocardial infarction with ST segment elevation	Valid N No Yes N missing						
Number of myocardial infarctions with ST segment elevation	Valid N Mean (SD) Median (Q1-Q3) Min-Max N missing						
Myocardial infarction without ST segment elevation	Valid N No Yes N missing						

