		Pulmonary embolism	Stable angina	Unstable angina	Myocardial infarction with ST segment elevation	Myocardial infarction without ST segment elevation
Treatment (VKA/NOAC/antiplatelet)	Valid N* No Yes N missing					
VKA	Valid N* No Yes N missing					
Type of VKA	Valid N Acenocoumarol Warfarin N missing					
NOAC	Valid N* No Yes N missing					
Type of NOAC	Valid N Dabigatran Rivaroxaban Apixaban Edoxaban N missing					
Antiplatelet	Valid N* No Yes N missing					
Type of antiplatelet	Valid N Aspirin Clopidogrel Prasugrel Ticlopidine Ticagrelor Cilostazol					

Document: H:\HOR-Europe\2019\2512352 - Study on anticoagulation management - BI\Proyecto\Estadistica\SAP\S AP_REBELD_version1.0_08072020.docx

Author: [REDACTED] Version Number: Version 1.0
Version Date: [08072020]

Template No.: RWI_TP_BIOS0013 Revision 1

Reference: RWI_WI_BIOS0015

Effective Date: 15Jun2018

		Pulmonary embolism	Stable angina	Unstable angina	Myocardial infarction with ST segment elevation	Myocardial infarction without ST segment elevation
	Triflusal Dipyridamole Others N missing					

*Number of events in each column

One event could be associated with more than one treatment

Table 48. Treatment received at the moment of bleeding events (1st part)

		Intracranial	Digestive	Genitourinary	Gingival
Treatment (VKA/NOAC/antiplatelet)	Valid N* No Yes N missing				
VKA	Valid N* No Yes N missing				
Type of VKA	Valid N Acenocoumarol Warfarin N missing				
NOAC	Valid N* No Yes N missing				
Type of NOAC	Valid N Dabigatran Rivaroxaban Apixaban Edoxaban N missing				
Antiplatelet	Valid N*				

Document: H:\HOR-Europe\2019\2512352 - Study on anticoagulation management - BI\Proyecto\Estadística\SAP\SAP_REBELD_version1.0_08072020.docx

Author: [REDACTED]

Version Number:

Version 1.0

Version Date:

[08072020]

Template No.: RWI_TP_BIOS0013 Revision 1

Reference: RWI_WI_BIOS0015

Effective Date: 15Jun2018

		Intracranial	Digestive	Genitourinary	Gingival
	No Yes N missing				
Type of antiplatelet	Valid N Aspirin Clopidogrel Prasugrel Ticlopidine Ticagrelor Cilostazol Triflusal Dipyridamole Others N missing				

*Number of events in each column

One event could be associated with more than one treatment

Table 49. Treatment received at the moment of thromboembolic events (2nd part)

		Nasal	Pulmonary	Articular-muscular	Conjunctival
Treatment (VKA/NOAC/antiplatelet)	Valid N* No Yes N missing				
VKA	Valid N* No Yes N missing				
Type of VKA	Valid N Acenocoumarol Warfarin N missing				

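### Hemorrhagic stroke is listed as a thromboembolic event, so the pooled thromboembolic rows include bleeds and the pooled bleeding rows can miss them

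*SAP*

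**What the plan says.** The protocol's covariate table (Section 9.3.3, Table 3) collects "History of thromboembolic events (Yes/No, number): TIA, ischemic stroke, hemorrhagic stroke, embolism systemic". The SAP (Section 11, Table 3) keeps the grouping and adds dates: "History of thromboembolic events (Yes/No, number and date): TIA, ischemic stroke, hemorrhagic stroke, embolism systemic". Its list continues with "deep vein thrombosis, pulmonary embolism, stable angina, unstable angina, myocardial infarction with/without ST segment elevation". The bleeding class is defined next: "and bleeding events (Yes/No, number and date): intracranial, digestive, genitourinary, gingival, nasal, pulmonary, articular-muscular, conjunctival".

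These lists feed four kinds of output:

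- **Pooled history rows.** Mock Tables 13 and 23 give a yes/no row for any thromboembolic event and a row for "Number of total thromboembolic events". Tables 14 and 24 do the same for bleeding. Tables 13 and 14 also carry a column of standardized differences, Pradaxa against the other NOACs.
- **Individual rows.** In the same tables each event type has its own yes/no row and its own count row.
- **Treatment at the event.** Hemorrhagic stroke is a column of Table 46 (thromboembolic). Intracranial bleeding is a column of Table 48 (bleeding).
- **Frailty model.** Section 14.6 relates frailty to age, sex and other factors "and the thromboembolic and the bleeding events (independent variables").

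SAP Section 11.1 refers all derived variables to Section 7.2. That section contains no derivation for either pooled event variable.

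**The concern.** In anticoagulated patients a thromboembolic history and a bleeding history say different things. The first suggests too little protection and the second too much anticoagulation. A pooled thromboembolic row that contains hemorrhagic strokes mixes the two. The protocol's background (Section 7) itself speaks of hemorrhagic and thromboembolic events as separate outcomes.

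The affected rows serve secondary objective 1, the description of patients by current NOAC. Protocol Section 9.9 says that standardized differences will be used to assess channeling. Prior bleeding and prior embolism are different reasons to choose one drug over another, so a blended row weakens that reading. A NOAC group with more bleeds recorded as hemorrhagic stroke would show more thromboembolism in the pooled row.

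**Working it through.** **Comparison of the lists.** The thromboembolic class has 10 items when the two types of myocardial infarction are counted separately. Hemorrhagic stroke and stable angina are among them. The bleeding class has 8 items, one of which is intracranial. I looked in SAP Sections 7.2, 8.4, 11 and 14.6 and in Tables 13, 14, 23, 24 and 46 to 49 for a rule that assigns hemorrhagic stroke to one class or removes duplicates. There is none. One intracerebral bleed can therefore be recorded in three ways:

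1. Only as hemorrhagic stroke. It enters the pooled thromboembolic rows and is absent from the pooled bleeding rows.
2. Only as intracranial. It is classified correctly.
3. As both. It enters both pooled classes and appears in both Table 46 and Table 48.

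**Size.** The documents state no event figure, so there is none to reproduce. The following is an illustration on assumed inputs. The only input from the documents is N = 500 (SAP Section 4.2). Assumptions:

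- h = share of patients with a hemorrhagic stroke, 0.5% to 2%
- t = share with any other thromboembolic event, 5% or 10%
- b = share with any other bleed, set equal to t
- h, t and b mutually independent

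Formulas, with T and B the two pooled flags and every hemorrhagic stroke entered in both classes:

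- P(T) = 1 − (1 − t)(1 − h), and P(B) likewise with b
- Share of T due only to a bleed = (P(T) − t) / P(T)
- P(T and B) = h + (1 − h)tb

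Worked case, h = 2% and t = b = 5%: P(T) = 1 − 0.95 × 0.98 = 0.069. The share is 0.019 / 0.069 = 27.5%. P(T and B) = 0.02 + 0.98 × 0.0025 = 0.02245. The odds ratio between the flags is 0.02245 × 0.88445 / 0.04655² = 9.16.

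| h | t = b | P(T) | Share of T due only to a bleed | Patients with both flags from one bleed (500h) | Odds ratio between flags |
|---|---|---|---|---|---|
| 0.5% | 5% | 5.48% | 8.7% | 2.5 | 3.01 |
| 0.5% | 10% | 10.45% | 4.3% | 2.5 | 1.50 |
| 1% | 5% | 5.95% | 16.0% | 5 | 5.04 |
| 1% | 10% | 10.90% | 8.3% | 5 | 2.01 |
| 2% | 5% | 6.90% | 27.5% | 10 | 9.16 |
| 2% | 10% | 11.80% | 15.3% | 10 | 3.04 |

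The P(T) and share columns do not need double entry; they hold whenever the bleed is recorded as hemorrhagic stroke. The last two columns do need it. If instead every such bleed is entered only as hemorrhagic stroke, the flags stay independent, but the pooled bleeding row reads 5% where 5.48% to 6.90% is correct, or 10% where 10.45% to 11.80% is correct. With hemorrhagic stroke counted only as a bleed, P(T) returns to t and the odds ratio to 1.

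**The case against.** The strongest reply is that little is lost. Every event type has its own row, so a reader can see hemorrhagic stroke separately, and in Table 13 it has its own standardized difference. The primary outcome, NOAC type and dose, does not use these variables. The SAP also follows the protocol's list. The reply on scope stands, and the point is confined to the pooled variables. It does not rescue them: the pooled yes/no percentage cannot be corrected by subtraction, because a patient may have both a hemorrhagic stroke and another listed event.

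Three stronger readings are tempting and are not supported:

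- **That bleeds will be counted twice.** This depends on the case report form and its completion rules, which are not in the documents. Nothing in the documents prevents double entry, but nothing shows that it occurs.
- **That the frailty model is misclassified.** Section 14.6 does not say whether events enter pooled or by type. If by type, the pooling does no harm there. If pooled and entered twice, the bleeding flag is still right and only the thromboembolic flag is wrong.
- **That stable angina inflates the row by a known amount.** No rates are given. Patients with stable angina may already be flagged through infarction or unstable angina, which the list also contains. Where coronary events belong is partly a choice of taxonomy, so this is a secondary matter.

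**Conclusion.** The concern holds for the pooled variables. Followed as written, the plan puts every recorded hemorrhagic stroke into the pooled thromboembolic yes/no and total (Tables 13 and 23) and into the Table 13 standardized differences on those rows. This does not depend on double entry. The pooled bleeding rows (Tables 14 and 24) are incomplete for any bleed entered only as hemorrhagic stroke. Double counting is possible, and an effect on the frailty model is conditional on pooled flags.

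On the assumed rates, 4% to 28% of patients flagged thromboembolic would owe the flag to a bleed alone. That range rests wholly on the assumptions shown and not on the documents. Individual event rows and the primary outcome are unaffected. The correction should be made because it bears on a secondary objective and costs little.

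Two smaller points belong with it. Stable angina is a chronic condition that overlaps the separate coronary artery disease item and does not suit an event count. The title "Table 49. Treatment received at the moment of thromboembolic events (2nd part") is wrong: the four columns of Table 49 are bleeding sites, and the table continues Table 48.

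**What to change.** 1. In SAP Section 7.2, add derivations for both pooled variables. Leave hemorrhagic stroke out of the thromboembolic yes/no and total, and count it in the bleeding yes/no and total.
2. Treat a hemorrhagic stroke and an intracranial entry in the same calendar month as one event after data review. Do not match on exact date: Section 8.4 sets a missing day to mid-month, so one bleed with a full date in one field and a partial date in the other would fail to match.
3. Apply the derivation in Tables 13, 14, 23 and 24. In Section 14.6, state whether events enter pooled or by type, and use the same derivation if pooled.
4. Show hemorrhagic stroke with the bleeding events in the treatment-at-event tables, moving it from Table 46 to Table 48.
5. Report stable angina as its own row outside the pooled event count, and retitle Table 49 as the second part of the bleeding events.
6. Log the change in Section 4.6.

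The cost is SAP wording, a regrouping in the program and a short data review of possible duplicates. Event type, number and date are already listed for collection in SAP Table 3. The downside is that the pooled totals will differ from the literal protocol list, which the Section 4.6 entry should explain. Individual rows stay as collected.

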11.1 Derivations

Derived variables are specified in section 7.2 Common Calculations on page 18 in this SAP.

12. MEDICATIONS

Medications will be presented for FAS. In the case of previous treatment with VKA, type, treatment duration will be presented.

Other concomitant treatments in the study visit (ARB or ACE inhibitor, Beta-blocker, Calcium channel blockers, Diuretics, Amiodarone, Statin, Proton pump inhibitor, H2-receptor antagonist, Digoxin, NSAIDs, Dronedarone, Other antiarrhythmics, ketoconazole (systemic), cyclosporine, itraconazole) will be presented.

History and current antiplatelet treatment will be described.

